[figure not shown]

## **SUMMARY**

The INNOVO Trial is a randomized controlled trial comparing giving ventilatory support with inhaled nitric oxide (INO) against ventilatory support without inhaled nitric oxide for neonates with severe but potentially reversible respiratory failure. The overall hypothesis to be tested is that adding INO to the ventilator gases reduces the risk of substantive adverse clinical outcomes, and is cost-effective. Previous work has suggested that INO can improve oxygenation in the short-term, but little reliable information is yet available about its long-term implications. A pilot INNOVO Trial has been conducted to guide the protocol for the main INNOVO Trial detailed here. Based on this experience the entry criteria will not be restrictive but will be allowed to reflect current clinical practice, with centres recruiting to the preterm, term and near term, or both strata.

The primary outcome measures are (a) death or severe disability at the age of one year (corrected), and (b) death or on supplemental oxygen on the expected date of delivery (or 28 days post-delivery for the full or near term babies). A total sample size of 200 preterm babies (<34 weeks) will be sufficient to reliably detect important effects on these outcomes and the 110 term or near term babies ( $\geq 34$  weeks) recruited over the same period will provide useful data which could be added to meta-analyses.

Sub-studies are also in place to consider other developmental and respiratory outcomes, cost-effectiveness, dose response of preterm babies, pathology, toxicology, respiratory function and views of trial participants.

## **BACKGROUND**

The problem to be addressed in this trial relates to the treatment of a particular group of newborn babies. Whereas the vast majority of babies born in 'developed' countries are healthy at birth, a small proportion are acutely ill. Appropriate and effective treatment at this time is crucial, as it has implications for an entire lifetime. Severe, but potentially reversible respiratory problems in the newborn are a major cause of death and there is an increased risk of subsequent morbidity in survivors. The care of these babies places major burdens on their families, and on the health services, both during the acute illness and in relation to any later problems.

An important aspect of the pathophysiology of lung disease in newborn babies is the persistence of pulmonary vasoconstriction. In utero this is the normal situation, but with the onset of respiration at birth pulmonary vasodilatation should occur leading to a fall in pulmonary vascular resistance and increased pulmonary blood flow. Where the presence of lung disease inhibits the processes involved in initiating this change (e.g. lung expansion, presence of oxygen within the lung) the pulmonary hypertension continues. More rarely persistent pulmonary hypertension of the newborn (PPHN) may arise in mature babies without evidence of lung disease. Modalities for the care of babies affected by pulmonary hypertension, with or without associated lung disease, may include ventilatory support, use of surfactant (particularly for preterm babies), maintenance of systemic blood pressure with inotropes, induction of alkalosis by hyperventilation and bicarbonate, sedation or muscle relaxation and, finally for term or near term babies, extracorporeal membrane oxygenation (ECMO). A variety of vasodilators have been used (e.g. tolazoline, prostacyclin and

magnesium sulphate) to help improve pulmonary blood flow but none has proved consistently effective and all have unwanted side effects, particularly systemic hypotension.

Inhaled nitric oxide (INO) is a promising therapy being used in a growing number of centres as part of the management of such babies. It is a highly diffusible, colourless gas with a vapour density similar to air. The nitric oxide (NO) molecule is considered a 'free radical' because it has an unpaired electron making it able to react with other molecules. NO is synthesised at a variety of sites in the human, including the vascular endothelial cells of the lungs. Endogenous NO production involves NO synthase, an enzyme which oxidises the terminal guanidino nitrogen atoms of the amino acid L-arginine. NO diffuses from the endothelium into the pulmonary vascular smooth muscle where it activates the soluble form of guanylate cyclase and increases the 'second messenger' cyclic guanosine monophosphate, resulting in pulmonary vasodilatation. There is some evidence that NO has an important role in the transition from fetal to 'adult' circulation at birth, and is a contributing factor in the normal decline in pulmonary resistance following delivery.

Exogenous NO has the obvious potential to improve pulmonary blood flow. It is also possible that pulmonary efficiency is improved as a result of better matching of ventilation and perfusion. NO has a very short half-life of about one to three seconds with a high affinity for binding with haemoglobin, after which it is quickly inactivated, resulting in the formation of methaemoglobin, inorganic nitrate and nitrite. Therefore systemic effects, including hypotension, are unlikely, on theoretical grounds, and this has been confirmed in open studies. There is, however, concern about its toxicity. Under the right conditions nitrogen dioxide and the free radical peroxynitrite may form. Peroxynitrite has been demonstrated to have a variety of adverse effects. High levels of nitrogen dioxide (formed by the combination of NO and oxygen) can be toxic to lung tissues, resulting in severe pulmonary oedema. In addition, NO has the ability to inhibit platelet aggregation, and therefore confers a risk of haemorrhagic complications. High concentrations of NO have been implicated in CNS effects (impaired memory and brainstem conduction time) in rats. Concern has also been expressed about possible carcinogenic effects, and inhibition of surfactant.

Both case series and trials (see below) indicate that INO may acutely improve oxygenation in babies born preterm (<34 weeks) with respiratory failure complicated by pulmonary hypertension, as well as those born at or near term ( $\geq 34$  weeks – henceforth referred to as 'mature') with PPHN, either as a primary condition of neonatal maladaptation or secondary to other diseases such as hyaline membrane disease (HMD), meconium aspiration, infection, and congenital diaphragmatic hernia. Rigorous information about the implications of these short-term effects on substantive clinical outcomes is, however, not yet available.

## **Evidence from trials**

*'Mature' babies.* A systematic review was published in the Cochrane Library. The last substantive update was in November 1997. The review was based on 8 trials, ranging in sample size from 17 to 235. All the trials provided data on the short-term effects on oxygenation, and confirmed that INO can, indeed, lead to significant improvements during treatment and up to one hour afterwards. Not all the trials provided data on substantive clinical outcomes. For instance, based on five of the trials, the review found that INO reduced the requirement for ECMO (Relative Risk (RR) 0.69; 95% Confidence Interval (CI) 0.56 to 0.85), reduced the risk of death or ECMO (RR 0.72 (95% CI 0.60 to 0.87)), but did not suggest any benefit of INO on mortality alone (RR 1.03; 95% CI 0.62 to 1.72), although this CI is wide. A further trial which has not yet been included in the review has come to similar conclusions. No

long term follow up information was available from any of the trials for this review, which did not report data about side-effects and toxicity. Nevertheless, the reviewers conclude: “On the evidence presently available it appears reasonable to use inhaled nitric oxide...for term and near term babies with hypoxic respiratory failure who do not have a diaphragmatic hernia”. We have commented on this in the Criticisms section of the Cochrane Library, making three main points: (1) There is a need for further information about longer term neurodevelopmental outcomes. (2) Reducing the need for ECMO may not represent an adverse outcome as, appropriately used, it has benefits both for mortality and for respiratory function, without leading to greater risk of neuro-developmental problems. In addition it is plausible that delaying the introduction of ECMO whilst INO is tried might, by increasing the time the baby is exposed to hypoxia, increase the rate of neurodevelopmental delay observed in survivors. (3) The effect of INO in reducing the use of ECMO may be an over-estimate as several of the trials were stopped early on the advice of data monitoring committees. Finer and Barrington do temper their conclusions by suggesting the need for further research to assess “what are the long term effects, if any, of INO on the developing lung and on the infant’s neurodevelopment...and to evaluate the benefit of INO in premature infants with hypoxic respiratory failure”.

More recently the trial Steering Committee discussed the information now available from a single trial. These data showed no evidence of difference in neurodevelopmental and behavioural outcomes in the 87% of surviving babies followed up. As this was a single trial, in a North American setting, the INNOVO Steering Committee decided sufficient uncertainty remained to continue to recruit ‘mature’ babies into the trial.

### **INNOVO pilot trial**

In the pilot, clinicians recruited babies into the trial if they were uncertain about the benefits of INO for babies in their care. Based on the first 64 babies, 40 were preterm (<34 weeks gestation at birth), and 24 were term or near term. The range of uncertainty in terms of level of severity was very variable, with an inter-quartile oxygenation index range of 17 to 45.

Many centres recruited in both gestational age categories, some recruited only preterm babies, some recruited term or near term babies. Rates of adverse outcomes in preterm babies in the pilot phase were very high, although not so high for ‘mature’ babies. This led to the conclusion that a definitive trial of preterm babies within a reasonable timeframe was feasible and a trial of ‘mature’ babies would produce useful data for meta-analysis.

## **Nitric oxide use**

Nitric oxide is becoming well established in neonatal clinical practice, especially for ‘mature’ babies. For example, a recent survey of the 27 ‘on-line’ centres in the pilot trial asked about ‘out-of-trial’ use of INO since coming ‘on-line’. Twenty replies were received. For preterm babies, although most centres had not used INO at all, or only once over this (variable) period, seven centres had used it more frequently, including a centre which had given INO to over 20 babies in the previous 15 months. For ‘mature’ babies, eight centres used INO for two or more babies, with two centres using it for more than 20 babies. It seems likely that use will be higher in centres which are not committed to The INNOVO Trial. Overall, this level of use of INO is worrying, given that the evidence from trials shows that the clinical effectiveness of INO has not yet been rigorously tested.

It is therefore imperative that the INNOVO main trial recruits readily to answer the crucial questions about the clinical and cost-effectiveness of INO before the window of opportunity closes.

## **THE AIMS OF THE TRIAL**

The aims of the trial are:

1. To assess the clinical effectiveness and cost-effectiveness of a policy of adding or not adding inhaled nitric oxide (INO) to the ventilator gases of neonates with severe respiratory failure.
2. To conduct relevant sub- studies (see below).

## **METHODS**

### **Eligibility - hospitals:**

Hospitals are eligible to participate if they are accustomed to providing long-term ventilatory support for newborn babies, have facilities for providing INO, and have research ethics committee approval to participate in the trial. Facilities for echocardiography are strongly preferred, in order to be able to exclude babies with congenital heart disease. Before being considered ‘on-line’ to recruit, centres have to be visited and taken through technicalities and procedures in the Trial Folder by the Trial Research Technician and/or the Trial Co-ordinator.

Detailed technical guidelines are provided in the Trial Folder. The part-time Trial Research Technician at the Clinical Co-ordinating Centre will travel to different centres, and be available to respond to queries in collaboration with the Technical Advisory Group.

### **Eligibility – babies:**

- (1) Uncertainty by the responsible clinician about whether the baby may benefit from INO. *It is strongly recommended that an echocardiograph is performed on ‘mature’ babies considered for trial entry. It is also advisable for preterm babies. Apart from babies undergoing*

*cardiothoracic surgery and/or with known congenital heart disease, most babies presently being treated with INO will be eligible for entry into the trial.*

- (2) Respiratory failure, requiring ventilatory support and administration of surfactant where appropriate. *The severity of illness of the baby will be indicated by the OI at recruitment. The pilot trial has shown considerable variation in the level of severity at which clinicians have felt uncertainty about the benefit of INO.*
- (3) Aged less than 28 days old. *The majority of babies recruited will be less than 72 hours of age, but there may be situations where babies acquire respiratory disease later in the neonatal period.*
- (4) No evidence of an uncorrectable\* bleeding disorder. *Platelet count must be >50,000 cells per mm^3 plus KPPT must be <72 secs or INR <2.*
- (5) No ultrasound evidence of intra-parenchymal lesions. *i.e. an echodense area (of at least equal echodensity to the choroid plexus or bone) involving the parenchyma of the brain and/or existing parenchymal lesions which are echo-poor, e.g. established porencephalic cysts.*
- (6) No contra-indication to continuation of treatment, known at trial entry. Examples may include severe congenital abnormalities, lethal chromosomal anomalies etc.

### **Trial entry:**

If the baby meets the eligibility criteria, the trial should be discussed with the baby's parents. Try to speak to both parents, if possible. *For centres taking part in the Views of Participants Study, tape the discussion if appropriate and if parents agree to the recording.* Discuss the trial with the parents and give them the Information for Parents leaflet. (NB there are separate versions, one for girls and one for boys). If possible, allow some time for consideration.

If the parent(s) agree to the baby's participation in the trial, complete part A of the trial datasheet (the entry form) and telephone the 24-hours-a-day, 7-days-a-week randomization service on

[name] (UK centres) [[name] (non-UK centres)].

After eligibility has been confirmed and the entry details have been recorded, a trial number and the random allocation (based on a minimisation algorithm) will be given, either:

- (1) 'Add NO to ventilatory gases' or
- (2) 'Ventilatory support without NO'.

Minimisation is based on the two gestational age groups: <34 weeks and ≥ 34 weeks

---

\* Amended from uncorrected to uncorrectable bleeding disorder at Steering Committee meeting held 22nd November 2000

*Minimisation categories for the <34 weeks gestational age group*

Centre

Principal diagnosis at trial entry: acute preterm lung disease (PLD), chronic PLD, other

Respiratory disease severity at trial entry: OI < 30, ≥30

Postnatal age: ≤3, 4-28 days

*Minimisation categories for the ≥ 34 weeks gestational age group*

Centre

Principal diagnosis at trial entry: congenital diaphragmatic hernia, primary persistent pulmonary hypertension of the newborn (PPHN), secondary PPHN, 'other'

Respiratory disease severity at trial entry: OI <40, ≥40

Postnatal age: ≤3, 4-28 days

After the allocation has been assigned, inform parent(s) as soon as possible and add a trial sticker to baby's notes.

**Outcomes:**

The primary outcomes will be:

- (1) (a) Death or severe disability at one year of age (corrected)
  - (b) Death by one year of age (corrected)
  - (c) Severe disability at one year of age (corrected), defined as no/minimal head control or inability to sit unsupported, or no/minimal response to visual stimuli as these have been found to be equivalent to a Developmental Quotient (DQ) of < 50.
- (2) (a) Death before discharge from hospital.
  - (b) chronic lung disease, defined as being on supplemental oxygen at the expected date of delivery (preterm stratum) and at 28 days post-delivery ('mature' stratum).

Outcome will be assessed at two points: at discharge from neonatal services (or prior death), and at one year of age (corrected).

Secondary measures of outcome will include:

At discharge from neonatal services (or prior death)

referral for ECMO support for 'mature' babies  
length of stay in hospital (neonatal unit and other wards)  
length of time on supplemental oxygen (in and out of hospital)  
length of time on ventilatory support

---

 Oxygenation Index (OI) = (mean airway pressure x FiO2) / Post-ductal Pa O2 mm Hg

pneumothorax or other pulmonary airleak  
pulmonary haemorrhage  
major cerebral abnormality as judged from ultrasound examination  
necrotising enterocolitis  
treatment of retinopathy of prematurity  
infection - suspected or confirmed  
age at which oral feeding is established

At the age of one year (corrected)

impairment and disability (neuromotor, vision, hearing, and development)  
respiratory problems (symptoms and lung function)  
seizures  
reduced growth.

Neurodevelopmental outcome will be assessed using a brief questionnaire for the local paediatrician caring for the baby to complete in the routine follow-up clinic. In this, information will also be sought on less severe degrees of impairment and disability in all fields of development, impairment and disability (neuromotor, vision, hearing, and development). After discussion with the local paediatrician, parents of appropriate babies able to cope with travel will be invited to bring their baby for a detailed respiratory function tests at London or Leicester.

Analyses will be based on the groups as allocated (the 'intention to treat' principle). All analyses will be stratified by gestational age at trial entry (<34 weeks and  $\geq$ 34 weeks). Additionally, the primary and principal secondary outcome measures will be stratified for the major prognostic variables: principal diagnosis leading to respiratory distress, postnatal age, and the severity of respiratory disease at trial entry. In this way, some information can be gained about the differential effects of INO in the different categories of babies recruited.

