### **Sample size:**

The size of the trial is calculated separately for babies born preterm, and 'mature' babies based on data from the pilot trial.

- a) Preterm babies: To detect whether INO reduces the primary outcome of death or severe disability at one year (corrected) from 60% to 40% (i.e. RR of 0.67) with  $\alpha$  of 0.05 (2-sided) and 80% power would require a total sample size of approximately 200 babies, which would also allow us to detect a reduction in the short term outcome from 75% to 55%.
- b) 'Mature' babies: Assuming recruitment of 'mature' babies ceases at the same time as for preterm babies, a further 86 'mature' babies are likely to have been recruited. The total sample size of 110 (including the 24 recruited in 1997/8) could detect whether INO could reduce the primary outcome of death or severe disability at one year (corrected) from 31.5% to 8.5% (i.e. RR of 0.27) with  $\alpha$  of 0.05 (2-sided) and 80% power, although recruitment of 110 'mature' babies would be sufficient to detect a reduction in the short term outcome from 70% to 40%.

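### The Summary, the Outcomes section and the sample size name different primary outcomes, and the short-term composite named in the Summary is missing from Outcomes

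*Protocol*

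**What the plan says.** Three places in the protocol describe the primary outcome.

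- **Summary.** Two composites: "The primary outcome measures are (a) death or severe disability at the age of one year (corrected), and (b) death or on supplemental oxygen". The second is timed at the expected date of delivery for preterm babies and at 28 days for term or near-term babies.
- **Methods, Outcomes.** Under "The primary outcomes will be" come two numbered groups with five lettered entries. Group (1) has (a) "Death or severe disability at one year of age (corrected", (b) "Death by one year of age (corrected" and (c) "Severe disability at one year of age (corrected), defined as no/minimal head control or inability to sit unsupported", with a visual criterion as a further alternative. Group (2) has (a) "Death before discharge from hospital" and (b) chronic lung disease, meaning supplemental oxygen at the same two time points as in the Summary. No entry is ranked above another.
- **Sample size.** One outcome is called primary: "To detect whether INO reduces the primary outcome of death or severe disability at one year (corrected) from 60% to 40"%, at two-sided 0.05 with 80% power and about 200 preterm babies. A short-term outcome is then said to be detectable too (75% to 55% preterm, 70% to 40% mature). The section does not define it.

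**The concern.** The number of primary outcomes is two, five or one, depending on the section. The sharpest conflict concerns the short-term outcome. The Summary makes it a composite of death or oxygen. Outcomes splits it into two stand-alone entries and gives no composite. The sample size powers something at 75% and 70% that Outcomes does not define.

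The split matters because oxygen status and severe disability can be observed only in babies who live. A treatment that saves lives adds survivors, who can then be on oxygen or disabled. Entries (1)(c) and (2)(b) can therefore move against the treatment while (1)(b) and (2)(a) move in its favour. A composite counts death as a failure and avoids this; stand-alone primaries do not. The protocol does not say which result decides the trial when the entries disagree.

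The secondary stake is the error rate. The stated 0.05 describes one test of one outcome. It would not describe a claim that could rest on any of several.

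**Working it through.** **1. The plan's own size.** Inputs from the sample size section: 60% v 40%, two-sided 0.05, 80% power. 1:1 allocation is assumed, because no ratio is stated.

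Per arm, n = [z(0.975)·√(2p̄q̄) + z(0.80)·√(p1q1 + p2q2)]² / (p1 − p2)²

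= [1.960 × 0.7071 + 0.8416 × 0.6928]² / 0.04 = (1.386 + 0.583)² / 0.04 = 96.9, so 97 per arm and 194 in total. This agrees with about 200.

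Power at 100 per arm: Φ[(0.20 × √100 − 1.386) / 0.6928] = Φ(0.886) = 81.2%.

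The other stated effects are also covered: 75% v 55% has 84.8% power at 200, 70% v 40% has 89.6% power at 110, and 31.5% v 8.5% gives exactly 110 with a continuity correction.

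**2. The sections side by side.**

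| Outcome | Summary | Outcomes | Sample size |
|---|---|---|---|
| Death or severe disability, 1 year | primary | primary (1)(a) | the primary outcome |
| Death by 1 year | – | primary (1)(b) | – |
| Severe disability, 1 year | – | primary (1)(c) | – |
| Death or oxygen | primary | absent | perhaps the short-term outcome |
| Death before discharge | – | primary (2)(a) | – |
| Oxygen alone | – | primary (2)(b) | – |

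Only the first row agrees throughout. The mortality window differs too: up to discharge in (2)(a), against a fixed date for the Summary's composite.

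**3. Direction of the survivor-only entries.** Illustrative rates, not in the protocol: 50% die before discharge and half of survivors are on oxygen. Then 0.50 × 0.50 = 25% of all babies are on oxygen, and the composite is 50% + 25% = 75%. If deaths fell to 40% with the same risk among survivors, 0.60 × 0.50 = 30% would be on oxygen and the composite would be 70%. Oxygen status worsens while mortality and the composite improve. With survivors as the denominator, the entry would worsen only if the extra survivors were sicker.

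**4. Error rate if any one entry at 0.05 counted as success.** With independent tests the rate would be 1 − 0.95² = 9.75% for two and 1 − 0.95⁵ = 22.6% for five. The five entries are nested, so 22.6% is too high. Null trials were therefore simulated: 40,000 per scenario, 100 per arm, pooled z tests at two-sided 0.05. Rates were anchored at about 60% for death or severe disability and 75% for death or oxygen, with death before discharge standing in for death in the latter. The split into components is assumed. Anchor check for the first row: 0.50 + 0.50 × 0.04 = 0.52 dead by one year; 0.52 + 0.48 × 0.17 = 0.602; 0.50 + 0.50 × 0.50 = 0.75.

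| Death before discharge | Later death | Severe disability in survivors | Oxygen in survivors | Two composites | Five entries |
|---|---|---|---|---|---|
| 50% | 4% | 17% | 50% | 8.9-9.4% | 16.8-17.1% |
| 40% | 5% | 30% | 58% | 9.5-9.6% | 16.8-17.4% |
| 55% | 2% | 9% | 44% | 8.7-8.8% | 14.9-16.2% |
| 30% | 5% | 40% | 64% | 9.5-9.7% | 17.4-17.6% |

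Each pair spans two denominators for severe disability and oxygen: survivors only, or all babies. Two further scenarios doubled the risk of later death and disability in babies on oxygen; they gave 8.8-9.1% and 16.6-17.6%. Overall: 8.7-9.7% for two and 14.9-17.6% for five. Interim looks are not included.

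**5. Cost of other ways to resolve it.** Splitting alpha equally over two outcomes (0.025 each, z = 2.241): Φ[(2 − 2.241 × 0.7071) / 0.6928] = Φ(0.599) = 72.5% power for 60% v 40% at 200 babies, or 236 babies to restore 80%. A fixed order leaves the first outcome at 81.2%.

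**The case against.** The strongest reply is that one long-term and one short-term outcome run through all three sections. Outcomes numbers only two groups. In group (1), (b) and (c) can be read as the components of (a); in group (2), death and oxygen are the elements of the Summary's second composite; the sample size deals with the same pair. Showing components beside a composite is also good practice, since it exposes the case where death falls and disability rises. Testing order and division of alpha are commonly left to the analysis plan, which is not shown.

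Much of this stands. The lettering may mean two outcomes with components, and the absence of a multiplicity rule is not a finding here. But the reading breaks down in group (2), which has no composite for its entries to be components of, and which counts deaths up to discharge. No analysis plan can make the three sections of the protocol agree.

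A reader might also infer that all five entries are tested at 0.05, that any one suffices, and that the trial's error rate is therefore well above 5%. The protocol does not say this. It gives 0.05 only in the sample size section, for death or severe disability and at most by implication for the short-term outcome. Nor does it support combining the strata, which under the same rule would give roughly 17-19% for two outcomes and 28-32% for five. The sample size section does quote power for mature babies, but the Summary and the pilot trial section give that stratum the role of supplying data for meta-analysis.

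**Conclusion.** The inconsistency is certain and can be read off the page. The Summary, Outcomes and Sample size sections give different primary outcomes, the death-or-oxygen composite is absent from Outcomes, and a powered short-term outcome is left undefined there. The consequence is that the protocol does not fix which result decides the trial, and two of the five entries can move against a life-saving treatment.

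The error rate is conditional. It reaches about 9-10% (two composites) or 15-18% (five entries) in the preterm stratum only if each is tested at two-sided 0.05 and one success is enough. It also rests on 1:1 allocation and on assumed component rates, though the range is narrow across the splits tried. The size of about 200 is right for the outcome it names. The point should be corrected, but it does not call the design into question.

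**What to change.** Make the three sections agree.

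- In Outcomes and the Summary, name (1)(a), death or severe disability at one year corrected age in the preterm stratum, as the primary outcome. The sample size section already treats it so.
- Replace group (2) with the Summary's composite of death or supplemental oxygen at the stated time point, and say by what date deaths count. Make it key secondary, or second in a fixed order, and use the same name in the sample size section.
- List death by one year, severe disability, death before discharge and oxygen status as components, reported descriptively.
- Report the mature stratum as estimates with confidence intervals, in line with its meta-analysis purpose.

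The change is to wording only; N stays at about 200 and power for (1)(a) at 81%. The small downside is that the short-term outcome could not carry a confirmatory claim on its own. If the sponsor wants that, two declared primaries with alpha split equally is also legitimate, at about 73% power for (1)(a) with 200 babies, or 236 babies for 80%. Either choice is acceptable if all three sections state it.

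### Within the preterm stratum, gestational age in weeks is neither a minimisation factor nor a named prognostic variable: some precision is lost and chance imbalance goes uncorrected, but there is no bias.

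*Protocol*

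**What the plan says.** Under Trial entry, "Minimisation is based on the two gestational age groups: <34 weeks and ≥ 34 weeks". Below 34 weeks the minimisation factors are:

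- centre
- diagnosis: "Principal diagnosis at trial entry: acute preterm lung disease (PLD), chronic PLD, other"
- oxygenation index (OI), cut at 30
- postnatal age: "Postnatal age: ≤3, 4-28 days"

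The analysis paragraph that closes the Outcomes section repeats the split: "All analyses will be stratified by gestational age at trial entry", with the same cut at 34 weeks. It adds that the primary and principal secondary outcomes will be "stratified for the major prognostic variables: principal diagnosis leading to respiratory distress, postnatal age, and the severity of respiratory disease at trial entry". Its stated purpose is that "some information can be gained about the differential effects of INO in the different categories of babies recruited".

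Under Sample size, about 200 preterm babies are planned to detect a fall in "death or severe disability at one year (corrected) from 60% to 40% (i.e. RR of 0.67") with 80% power at two-sided 0.05. No covariate enters that calculation.

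**The concern.** All babies below 34 weeks form one stratum, and nothing in allocation or in the named analysis variables separates the least mature from those just under the cut. Postnatal age counts days since birth and is not a measure of maturity.

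The protocol treats gestation as a main divider of risk. It has separate minimisation schemes and separate sample sizes on either side of 34 weeks. The assumed control risk of death or severe disability is 60% below the cut and 31.5% above it.

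The short-term outcome is also tied to gestation. Oxygen dependence in preterm babies is judged at the expected date of delivery. Taking that date as 40 weeks, a baby born at 24 weeks is assessed about 16 weeks after birth and one born at 33 weeks about 7 weeks after birth.

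If gestation predicts outcome within the stratum, leaving it out gives up precision. If the arms happened to differ in maturity, the planned analysis would have no pre-specified answer, and an adjustment chosen afterwards would be open to dispute.

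**Working it through.** **1. The plan's own figure.** Inputs from Sample size: 60% v 40%, two-sided 0.05, 80% power. Equal allocation is assumed.

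Per arm: n = [1.96·√(2·0.5·0.5) + 0.8416·√(0.6·0.4 + 0.4·0.6)]² / 0.20² = (1.3859 + 0.5831)² / 0.04 = 96.9. This rounds up to 97, or 194 in total, which agrees with about 200.

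Power at 100 per arm: Φ[(0.20·√100 − 1.3859) / 0.6928] = Φ(0.886) = 81.2%.

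The stated size therefore reproduces for an unadjusted comparison of two proportions.

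**2. Assumptions.** The protocol gives neither the spread of gestation below 34 weeks nor its relation to outcome. Assumed: completed weeks 23 to 33, mean 27.6, SD 2.28, marginal risks held at 60% and 40%, and an odds ratio (OR) per extra week from 0.9 to 0.6.

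**3. Power with and without gestation in the model.** Logistic model, 100 per arm, Wald test, 20,000 simulated trials per row. The last column is the change in a separate run of 4,000 trials.

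| OR per week | Control-arm variance explained | Unadjusted | Adjusted | Change (points) | Change, 4,000 trials |
|---|---|---|---|---|---|
| 0.90 | 1% | 82.6% | 81.7% | −0.9 | −1.1 |
| 0.80 | 6% | 82.8% | 83.6% | +0.8 | +0.3 |
| 0.75 | 9% | 82.1% | 83.9% | +1.8 | not run |
| 0.70 | 13% | 83.0% | 86.2% | +3.2 | +2.8 |
| 0.60 | 22% | 83.0% | 89.5% | +6.5 | +7.5 |

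So the range is about −1 to +7 points. Rounding the 4,000-trial powers to 83% and 91% would make the top end look like 8; the unrounded gap is 7.5. The loss of about 1 point at 0.90 also appears when gestation has no effect at all. It is the price of an idle term.

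As equivalent numbers, 200·(1 − variance explained) gives 197, 189, 174 and 156 adjusted babies matching 200 unadjusted at OR 0.9, 0.8, 0.7 and 0.6.

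**4. Chance imbalance.** The SE of the between-arm difference in mean gestation is 2.28·√(2/100) = 0.32 week. The two-sided 1-in-20 bound is 1.96·0.323 = 0.63 week. Multiplying by the fall in control risk per week:

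- OR 0.9: 0.63·2.5 = 1.6 points
- OR 0.8: 0.63·5.0 = 3.2 points
- OR 0.7: 0.63·7.5 = 4.7 points
- OR 0.6: 0.63·9.6 = 6.1 points

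**5. Validity of the unadjusted test.** With no treatment effect, the unadjusted test rejected in 4.6% to 5.7% of the 4,000-trial runs, so the error rate holds.

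These figures are for death or severe disability. The short-term composite was not simulated.

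**The case against.** **The covariate set is usually left to the SAP, which is not shown.** Silence here would be no finding. But the protocol is not silent: it names a list and calls it the major prognostic variables. An SAP could still extend that list, which keeps the point modest.

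**The list may define subgroups, not covariates.** The next sentence speaks of differential effects, so this is a fair reading. If it is right, the protocol fixes no adjustment at all. If the list does mean adjustment, the unadjusted powers above are the wrong baseline, and what matters is the gain beyond diagnosis, postnatal age and severity. That gain was not calculated, and the documents give nothing to calculate it from. Diagnosis and OI may well carry part of the gestation effect. This stands and makes the figures an upper guide. On either reading, gestation in weeks is absent.

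**The contrast of 60% with 31.5% is not a slope below 34 weeks.** Correct. The cut also separates diagnoses, treatment options and dosing. The contrast makes a gradient plausible but does not measure one.

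**Imbalance and lost precision are one quantity seen twice.** Also correct: the confidence interval already allows for chance imbalance, so the two should not be added.

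A reader might go further and infer that the comparison is biased, that the trial is underpowered, or that gestation is ignored altogether. The documents support none of these. The test keeps its error rate, planned power is met, and both primary time points (expected date of delivery, one year corrected) are set by maturity. Nor is there support for a large gain: a correlation of 0.5 would give 90.9% power, but nothing in the protocol points to that value. An OR of 0.6 per week already implies a 0.6^10, or about 165-fold, range of odds across 23 to 33 weeks.

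**Conclusion.** The point holds as a small improvement in precision and robustness. Gestation in weeks is missing from both lists that govern the preterm comparison, although the trial must establish gestation to place each baby in a stratum.

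Under the assumed distribution and strengths, adjustment is worth about −1 to +7 power points. At odds ratios of 0.75 to 0.7 per week it is worth about 2 to 3, and less where the three named variables overlap with gestation. A 1-in-20 imbalance would move the estimate by about 2 to 6 points of the 20-point target. All of these sizes rest on assumed inputs. Nothing the protocol states is numerically wrong, and the sample size needs no change.

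**What to change.** In the analysis paragraph of the Outcomes section, add gestational age at birth (completed weeks, continuous) to the named prognostic variables. State that in the preterm stratum it is a pre-specified covariate, alongside diagnosis, postnatal age and severity, for both primary composites: death or severe disability at one year corrected, and death or supplemental oxygen at the expected date of delivery. Report a standardised risk difference or relative risk, so that the estimate is on the same footing as the planned 60% v 40%, with the unadjusted result beside it.

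The cost is one sentence, one model term and the computation of a marginal effect. No extra babies or visits are needed. The entry datasheet is not shown, but birth date and expected date of delivery, which the outcome definitions already require, give gestation. At an average risk of 50%, 200 babies yield about 100 events. Six terms (treatment, two for diagnosis, one each for postnatal age, severity and gestation) leave about 100/6 ≈ 17 events per term. If gestation is only weakly prognostic, there will be little or no gain.
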